### 7.3.2 Pralatrexate

Patient treated with pralatrexate are at risk of developing mucositis. The risk of developing mucositis can be lowered by pretreating patient with leucovorin 15 mg PO BID that has to be held the day before, day of and day after pralatrexate administration. The treatment with leucovorin will be given with treatment as noted above but can be given at the treating physician's discretion for pralatrexate related mucositis (i.e. in schedule delays). Pralatrexate and decitabine can induce hematologic toxicity that should be address with Neupogen/Neulasta support at the treating physician's discretion and as suggested in Table 12 and Table 13.

Doses may be omitted or reduced based on patient tolerance. Omitted doses will not be made up for at the end of the cycle; once a dose reduction occurs for toxicity, there will be no re-escalation. For dose modifications and omissions, use the suggested guidelines in Table 11, Table 12 and Table 13 below.

Table 11: Suggested Guidelines for Pralatrexate Dose Modifications for Mucositis after Cycle 1

Mucositis Grade a on the Day of Treatment	Action	Dose upon recovery to Grade ≤ 1
Grade 2	Omit dose	Maintain dose level
Grade 2 recurrence	Omit dose	Reduce to one dose level below
Grade 3	Omit dose	Reduce to one dose level below
Grade 4	Stop therapy	No further treatment with pralatrexate

a Per NCI CTCAE, Version 3.0

Table 12: Suggested Guidelines for Pralatrexate Dose Modifications for Hematologic Toxicities

Blood Counts on the Day of Treatment	Duration of Toxicity	Action	Dose upon re-start
Platelets < 50,000/µL	1 week	Omit dose	Continue prior dose
	2 weeks	Omit dose	Reduce to one dose level below
	>2 weeks	Stop therapy	No further pralatrexate
ANC 500-1,000/µL and no fever	1 week	Omit dose	Continue prior dose
ANC 500-1,000/µL with fever (a single temperature of > 38.3°C or sustained temperature of ≥ 38°C for over one hour) or ANC <500/µL	1 week	Omit dose, give G-CSF or GM-CSF	Continue prior dose with G-CSF or GM-CSF support
	2 weeks or recurrence	Omit dose, give G-CSF or GM-CSF	Reduce to one dose level below with G-CSF or GM-CSF support
	>2 weeks or 2nd recurrence	Stop therapy	No further pralatrexate

Table 13: Suggested Guidelines for Pralatrexate Dose Modifications for All Other Treatment Related Toxicities

Toxicity Grade a on the Day of Treatment	Action	Dose upon recovery to Grade ≤ 2
Grade 3	Omit dose	Reduce to one dose level below
Grade 4	Stop therapy	No further pralatrexate

a Per NCI CTCAE, Version 3.0)

### 7.4 Timing of Dose Administration

Trial treatment should be administered on Day 1 of each cycle after all procedures/assessments have been completed as detailed on the Trial Flow Chart (Section 8.0). Trial treatment may be administered up to 2 days before or after the scheduled Day 1 of each cycle due to administrative reasons.

All trial treatments will be administered on an outpatient basis.

Pembrolizumab 200 mg will be administered as 30-minute IV infusion every 3 weeks (21 days). Sites should make every effort to target infusion timing to be as close to 30 minutes as possible. However, given the variability of infusion pumps from site to site, a window of -5 minutes and +10 minutes is permitted

(i.e., infusion time is 30 minutes: -5 min/+10 min). Pralatrexate will be administered as a 3-5 minute IV infusion at day 1, day 8 and day 15 of a 28-day cycle. Decitabine will be administered as a 1-hour (+ 60 minutes) IV continuous infusion from day 1 to day 5 of a 28-day cycle.

In Arm A, pembrolizumab should precede the administration of pralatrexate on the days that both infusions are scheduled (refer to trial schema in section 5.1). In Arm B, decitabine should be infused first, pembrolizumab second and pralatrexate third when the three drugs are given together. On days where pembrolizumab is not due, decitabine should precede pralatrexate. When only two drugs are scheduled on the same day, decitabine should be infused first followed by pembrolizumab and pralatrexate should always be infused last (refer to trial schema 5.1). In Arm C, decitabine should precede the administration of pembrolizumab (refer to trial schema 5.1).

The Pharmacy Manual contains specific instructions for the preparation of the pembrolizumab infusion fluid and administration of infusion solution.

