### **5.2.2 Pralatrexate**

In Arm A, pralatrexate will be administered at the entry dose of  $30 \text{ mg/m}^2$  day 1, 8, 15 Q4W which represents the MTD identified in the PROPEL trial. Allocation of participants to doses of Pralatrexate will be conducted according to the study design described in [Section 10: Statistical Considerations](#).

In Arm B, pralatrexate will be administered at the entry dose of  $20 \text{ mg/m}^2$  day 1, 8, 15 Q4W and subsequently de-escalated (if applicable) following the study design described in the Statistical Considerations.

All patients receiving pralatrexate will receive folic acid at the dose of 1,000 mg orally daily and vitamin B12 intramuscularly every 2 cycles (8 weeks) as recommended in the package insert of the product. The vitamin supplementation will start prior to the first dose of pralatrexate as recommended in the drug package insert. Leucovorin will be used to decrease the risk of mucositis in all patients receiving treatment with pralatrexate. Leucovorin will be given at the dose of 15 mg orally twice daily and should be held the day before, the day of and the day after pralatrexate treatment. Leucovorin is mandatory for patients on trial.

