## 6.2 Trial Treatments

The treatment arms to be used in this trial are outlined in Table 7, Table 8 and Table 9 below.

Table 7: Trial Treatment – Arm A

Agent	Premedication Precautions	Dose	Route	Schedule A	Cycle Length
Pembrolizumab	N/A	200 mg (flat dose)	IV Administered first during cycle 1	Days 1*	Q3W
Pralatrexate	B12 and Folate supplementation (to be started within one week before initiation of treatment), and leucovorin (LV) as outlined	20 or 30 mg/m  **	IV push	Days 1, 8, 15	Q4W

\*Day 1 for pembrolizumab administration refers only to cycle 1 of treatment. Pembrolizumab will be continued every 3 weeks following the first administration.

\*\* Doses as appropriate for assigned dose level. Pralatrexate dose will be calculated using weight at cycle 1 day 1, unless weight has changed more than 10%. If so, the total dose should be calculated on the updated weight.

Table 8: Trial Treatment – Arm B

Agent	Premedication Precautions	Dose	Route	Schedule B	Cycle Length
Decitabine	Antiemetic	10 mg/m  *	IV	Days 1, 2,3,4,5	Q4W
Pralatrexate	B12 and Folate supplementation (to be started within one week before initiation of treatment) and leucovorin (LV)	20 mg/m  *	IV push	Days 1,8,15	
Pembrolizumab	N/A	200 mg (Flat dose)	IV	Day 8**	Q3W

\* Doses as appropriate for assigned dose level. Pralatrexate and decitabine dose will be calculated using weight at cycle 1 day 1, unless weight has changed more than 10%. If so, the total dose should be calculated on the updated weight.

\*\*Day 8 for pembrolizumab administration refers only to cycle 1 of treatment. Pembrolizumab will be continued every 3 weeks following the first administration.

Table 9: Trial Treatment – Arm C

Agent	Premedication Precautions	Dose	Route	Schedule C	Cycle Length
Pembrolizumab	N/A	200 mg (flat dose)	IV (Administered first during cycle 1)	Days 8*	Q3W
Decitabine	Antiemetic	20 mg/m  **	IV	Days 1,2, 3, 4, 5	Q4W

*\*Day 8 for pembrolizumab administration refer only to cycle 1 of treatment. Pembrolizumab will be continued every 3 weeks following the first administration.*

*\*\*Doses as appropriate for assigned dose level. Decitabine dose will be calculated using weight at cycle 1 day 1, unless weight has changed more than 10%. If so, the total dose should be calculated on the updated weight.*

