X Cycle 1 only. Additional pharmacokinetics sample (only for patients at UVA) will be obtained at day 5 to determine drug steady state.

X Decitabine will be given from day 1 to day 5 (or day 3, depending on dose level) of each cycle as described in section 5.2.3

X Pembrolizumab will be administered every 3 weeks (Q3W). In Arm B, pembrolizumab administration will be started on day 8 of cycle 1 as described in section 5.2.1.

X For cycle 1 day 1, laboratory screening tests can be considered valid for treatment on cycle 1 day 1 as long as they are performed within the screening laboratory test window (10 days). After Cycle 1, pre-dose laboratory procedures can be conducted up to 72 hours prior to dosing.

X Pharmacokinetics (PKs) and correlative study blood draws at Days 8 and 15 in a cycle are only for Cycle 1 (not cycles 4, 7, etc.)

X For subjects who have an allogeneic SCT within 24 months of last study treatment, transplant parameters will be collected and specific events will be collected for 18 months from the date of the allogeneic transplant to include graft-versus-host-disease (acute and/or chronic), veno-occlusive disease, febrile syndrome (a steroid-requiring febrile illness without an infectious cause), and encephalitis, for all grades, and regardless of relationship to study drug. Additional medically important adverse events post-allogeneic SCT may be submitted at the Investigator's discretion.

X Thyroid blood tests are only required every other cycle (e.g. day 1 only for odd cycles)

X After cycle 2, the day 22 CBC with differential is not required (e.g. not for cycles 5, 8, etc.)

X After 30 day safety visit, only new SAEs considered related to study intervention need to be collected and assessments (as applicable) may be by phone or videoconference. Active AEs at the time of 30 day safety visit should be followed through resolution or stability.

X See table in [section 9.1.7](#) for list of tests to include (not just the comprehensive metabolic panel)

X CBC with differential at Day 22 is for cycle 1 only (e.g. not for cycles 4, 7, etc)

STUDY FLOW CHART – ARM C	Treatment Cycle/Title:	Treatment Cycles 								Post-treatment			
		Screening (Visit 1)	1&4				2&5		3 &6		Discon	Safety Follow-up	Follow Up Visits
			D1	D8	D15	D22	D1	D22	D1	D15			

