### **9.1.10 Subject Registration and Randomization**

All participants must sign the consent form prior to determination of eligibility for this study.

When a site is ready to enroll a patient, the following documentation must be scanned and emailed to the UVA Coordinating Center:

- Patient and staff signed signature page of the current informed consent form (ICF)
- Completed Inclusion/Exclusion checklist demonstrating subject eligibility
- Supporting documentation needed to confirm eligibility (lab results, scan results etc.)

Consult the Study Reference Manual for instructions on sending this information. The Coordinating Center will consult with the Overall Study PI if questions arise in confirming eligibility. The UVA Coordinating Center will communicate the subject number and treatment dose assignment to the enrolling site.

Registration will occur following verification of eligibility by the treating physician.

Participants who are consented and accrued to the study should be registered in OnCore in accordance with the Clinical Trial Management System Policy via the UVa OnCore Resources link in Oncore. General guidelines are available in the OnCore User Manual and Data Entry Guide.

Participants should receive their first study treatment within 2 weeks of registration.

Treatment allocation will be discussed with participants during the process of informed consent and will occur after registration. Treatment allocation will be based upon the study design until a safety bound has been triggered or target accrual has been met. Arm allocation slots are generated by the coordinating center. Treatment allocation will occur after registration and within 2 weeks of the start of treatment.

This study does not involve any blinding or masking procedures. Subjects will be told which treatment they are receiving.

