## **10.0 STATISTICAL CONSIDERATIONS**

### **10.1 Study Design**

This is a Phase Ib study evaluating the safety and efficacy of pembrolizumab combined with pralatrexate (Arm A) or decitabine (Arm C) or decitabine and pralatrexate (Arm B) in patients with peripheral T-cell lymphoma (PTCL) and cutaneous T-cell lymphoma (CTCL). In all arms, toxicity will be assessed according to the NCI Common Toxicity Criteria for Adverse Events (CTCAE), version 5.0. Dose-limiting toxicity (DLT) is a binary outcome (yes/no) and will be determined by adverse events occurring during the first cycle of treatment (see Section 5.3 for DLT definition). In all arms, the maximum tolerated dose (MTD) is defined as the dose combination with a DLT rate closest to the target DLT rate of 25%. The study will accrue participants in cohorts of size 1 in all arms. After accrual of a participant to an arm, the accumulating DLT data will be used to update the model-based estimated DLT

probabilities for each dose level. These estimates will then be used to update the recommended dose level for the next participant accrued to that arm of the study.

Arms A and C:

The primary objectives of Arms A and C is to determine the MTD, defined by acceptable toxicity, of decitabine (Arm C) or pralatrexate (Arm A) (plus a fixed dose of pembrolizumab) from among the 3 study dose levels in the following tables, and to evaluate efficacy, as determined by overall response rate, at the estimated MTD.

Arm A		
Dose Level	Pralatrexate	Pembrolizumab*
Level 1 (start)	30 mg/m  day 1, 8, 15	200 mg day 1
Level -1	30 mg/m  day 1, 15	200 mg day 1
Level -2	20 mg/m  day 1, 15	200 mg day 1

Arm C		
Dose Level	Decitabine	Pembrolizumab*
Level 1 (start)	20 mg/m  day 1->5	200 mg day 8
Level -1	20 mg/m  day 1->3	200 mg day 8
Level -2	10 mg/m  day 1->3	200 mg day 8

Based on the accumulated data from the previous 5 subjects (1 observed DLT) accrued to Arm A, the first eligible subject in Arm A will be entered onto Level 1. Based upon the accumulated data from the previous 4 subjects (2 observed DLTs) accrued to Arm C, the first eligible subject in Arm C will be entered onto Level -1.

Arm B:

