The primary objective of Arm B is to determine the MTD, defined by acceptable toxicity, of pembrolizumab combined with decitabine and pralatrexate from among the six study dose combinations in the following table, and to evaluate efficacy, as determined by overall response rate, at the estimated MTD. In a previous version of the protocol (dated 14 Dec 2022), fifteen dose combinations were considered for Part B. While the current protocol version reduces the number of dose combinations to six, we have maintained the original combination labels to maintain consistency with the original dose levels for each combination.

Combination designation			
Pralatrexate	20mg/m  1,8,15	Combination 6	Combination 8
	20mg/m  1,15	Combination 3	Combination 5
	15mg/m  1,15	Combination 1	Combination 2
		10mg/m  1-3	10mg/m  1-5
		Decitabine	

Based on the accumulated data from the first 4 subjects (1 observed DLT) accrued to Combination 8 in Arm B, the next eligible subject in Arm B will be entered onto Combination 8.

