$$L_m(\theta_m) = \prod_{i \in \{1, 2, 3, 5, 8\}} \left( p_{mi}^{\exp(\theta_m)} \right)^{y_i} \left( 1 - p_{mi}^{\exp(\theta_m)} \right)^{n_i - y_i},$$

$y_i$  = the number of DLTs, and  $n_i$  = the number of treated patients in combination  $i$ . The ordering  $h$  with the largest likelihood is chosen and, within this ordering, DLT probability estimates are updated for each combination. If there is a tie between the likelihood values of two or more orderings, then the selected ordering  $h$  is randomly chosen from among the tied orderings. After accrual of each patient cohort into the trial, the DLT probability estimates,  $\tilde{R}(d_i)$ , are updated via

$$\tilde{R}(d_i) = p_{hi}^{\exp(\tilde{\theta}_h)}; \quad \tilde{\theta}_h = \arg \max L_h(\theta_h).$$

The DLT probability estimates are used to sequentially allocate participants according to the following rules:

1. If the most recent participant accrued to the study **does not** experience a DLT, then the recommended combination for the next participant will be the combination indicated by the model to have an estimated DLT rate closest to 25%. Escalation of both agents simultaneously or escalation of more than one dose level of either agent is not allowed.
2. If the most recent participant accrued to the study **does** experience a DLT:
  - a. If the DLT is mucositis or thrombocytopenia or mucositis plus neutropenia and/or thrombocytopenia, then the recommended combination for the next participant will be restricted to either the current combination administered to the most recent participant or to de-escalation of one dose level of Pralatrexate, based on which combination has an estimated DLT rate closest to 25%.
  - b. If the DLT is neutropenia or neutropenia and thrombocytopenia, then the recommended combination for the next participant will be restricted to either the current combination administered to the most recent participant or to de-escalation of one dose level of Decitabine, based on which combination has an estimated DLT rate closest to 25%

The study will sequentially repeat the estimation procedure after the enrollment and follow-up of each cohort. The allocation procedure will be repeated until sufficient information about the MTD has been obtained according to the stopping rules described below.

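### Section 7.4, Tables 7–8 and the Arm A/B flow charts give pralatrexate on day 8 at every dose level, but in Section 10.1 the first pralatrexate reduction consists only of dropping day 8

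*Protocol*

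**What the plan says.** **Operational sections.** Section 7.4 states: "Pralatrexate will be administered as a 3-5 minute IV infusion at day 1, day 8 and day 15 of a 28-day cycle". The same paragraph gives decitabine from day 1 to day 5, also unqualified. Tables 7 and 8 in Section 6.2 list pralatrexate on days 1, 8 and 15. Their footnote, "Doses as appropriate for assigned dose level", is marked on the dose entry and goes on to weight-based dose calculation. The Arm A and Arm B flow charts in Section 8.0 mark pralatrexate at D1, D8 and D15 of each cycle, with no footnote on that row. For decitabine the same flow charts do carry an exception: "Decitabine will be given from day 1 to day 5 (or day 3, depending on dose level) of each cycle".

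**Dose levels.** Section 10.1 sets the Arm A MTD search "from among the 3 study dose levels in the following tables". Only Level 1 has pralatrexate on days 1, 8 and 15; Levels -1 and -2 use days 1 and 15. In the Arm B grid, Combinations 6 and 8 use days 1, 8 and 15, while Combinations 1, 2, 3 and 5 use days 1 and 15. After 1 DLT in 4 participants on Combination 8, "the next eligible subject in Arm B will be entered onto Combination 8".

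**Linking text.** Section 5.2.2 presents days 1, 8 and 15 as the entry regimen for Arm B, to be "subsequently de-escalated (if applicable) following the study design described in the Statistical Considerations". Section 9.1.10 adds: "The UVA Coordinating Center will communicate the subject number and treatment dose assignment to the enrolling site".

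**The concern.** In this design a dose level is an amount and a set of days. For the first pralatrexate reduction the amount does not change, and the missing day 8 is the entire reduction. The sections that tell a site what to give on which day leave day 8 in.

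The operational sections cannot be read as describing the starting regimen only. Table 7 lists 20 or 30 mg/m² on days 1, 8 and 15, but in Arm A 20 mg/m² exists only at Level -2, on days 1 and 15. Table 7 therefore shows a reduced dose on a schedule that is not an Arm A level. The flow charts already make the decitabine days depend on dose level, so a reader would expect a similar note for pralatrexate if its days varied.

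Two things are at stake. A participant allocated to a lower level after a pralatrexate-type DLT could receive the unreduced pralatrexate schedule. That participant's outcome would then enter the POCRM likelihood as Combination 5 although the treatment given was that of Combination 8. Participants already on Combination 8 are affected too: Tables 11–13 tell the site to go one dose level below, which for pralatrexate means omitting day 8, while the flow chart still marks it.

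**Working it through.** **1. Pralatrexate per 28-day cycle** (mg/m² per dose × number of doses; levels from Section 10.1, three-day schedule from Section 7.4)

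| Level | Per 10.1 | With days 1, 8, 15 | Ratio |
|---|---|---|---|
| Arm B, Combinations 8 and 6 | 20 × 3 = 60 | 60 | 1.0 |
| Arm B, Combinations 5 and 3 | 20 × 2 = 40 | 20 × 3 = 60 | 1.5 |
| Arm B, Combinations 2 and 1 | 15 × 2 = 30 | 15 × 3 = 45 | 1.5 |
| Arm A, Level 1 | 30 × 3 = 90 | 90 | 1.0 |
| Arm A, Level -1 | 30 × 2 = 60 | 30 × 3 = 90 | 1.5 |
| Arm A, Level -2 | 20 × 2 = 40 | 20 × 3 = 60 | 1.5 |

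The intended first step cuts pralatrexate by one third (60 to 40, or 90 to 60). On the three-day schedule the cut is zero: Combination 5 becomes Combination 8, Combination 3 becomes Combination 6, and Level -1 becomes Level 1. At Combinations 1 and 2 and at Level -2 the excess is still 50%, but the starting regimen is not recreated.

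**2. How close Arm B is to using such a level** (model and rules of Section 10.2)

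The estimated DLT rate is the skeleton value raised to a power c = exp(θ). All Arm B data so far are at Combination 8, whose skeleton value is 0.25 in all five orderings. The orderings therefore tie in likelihood, and the maximum likelihood estimate sets 0.25^c equal to the observed rate, so c = ln(rate)/ln(0.25). Combination 5 has skeleton value 0.11 or 0.174, depending on the ordering.

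- *DLT in participant 5 (2/5).* c = ln(0.4)/ln(0.25) = 0.661. Combination 8: 0.400, distance from 0.25 = 0.150. Combination 5: 0.11^0.661 = 0.232 (distance 0.018) or 0.174^0.661 = 0.315 (distance 0.065).
- *No DLT in participant 5 (1/5).* Combination 8 is estimated at 0.20 and every other combination lower, so Combination 8 stays closest to 0.25 and participant 6 is treated there.
- *DLT in participant 6 (2/6).* c = ln(0.333)/ln(0.25) = 0.7925. Combination 8: 0.333, distance 0.083. Combination 5: 0.11^0.7925 = 0.174 (distance 0.076) or 0.174^0.7925 = 0.250 (distance 0.000).

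If the DLT is mucositis or thrombocytopenia, rule 2a limits the choice to the current combination or one pralatrexate level lower, that is, Combination 8 or 5. Combination 5 is closer to 25% in both cases and under either skeleton value, so the random tie-break between orderings does not matter.

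**3. How often days 1, 15 combinations are used in the protocol's own simulations** (Section 10.5, Arm B, scenarios 1 to 5)

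| | S1 | S2 | S3 | S4 | S5 |
|---|---|---|---|---|---|
| Mean participants, Combinations 3 + 5 | 1.08 | 1.38 | 0.40 | 3.66 | 4.62 |
| Mean participants, Combinations 1 + 2 + 3 + 5 | 1.25 | 1.61 | 0.43 | 5.05 | 7.99 |
| MTD among Combinations 1, 2, 3, 5 (%) | 6.1 | 7.7 | 1.0 | 37.3 | 57.3 |

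Each entry is a sum over the printed cells. For scenario 5, Combinations 3 + 5: 2.09 + 2.53 = 4.62; adding Combinations 1 and 2: 4.62 + 1.06 + 2.31 = 7.99; selection: 18.38 + 13.10 + 6.94 + 18.90 = 57.32%.

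**The case against.** A dosing error is far from certain. The labels Combination 5 and Level -1 are defined only in Section 10.1, together with their days. Participants enter one at a time and the Coordinating Center sends each assignment, so a site told Combination 5 would normally look it up there. Section 5.2 places administration details in 5.2.1–5.2.3, and 5.2.2 treats days 1, 8 and 15 as the entry regimen. Section 7.4 mainly covers infusion times and drug order and names no arm for its pralatrexate sentence. The footnote to Tables 7 and 8 can be read as covering days, because a dose level in 10.1 includes days.

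This lowers the probability of an error. It does not remove the conflict. Section 9.1.10 does not say that the assignment specifies days. The flow charts are arm-specific, are the natural source for scheduling visits, and qualify decitabine but not pralatrexate. The table footnote is attached to the dose and is followed by weight-based calculation.

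Three further points stand. Arm B opens only after Arms A and C finish enrolling and already has four participants, so the Arm A contrasts probably affect few or no new allocations, although Section 10.4 still lists five more for Arm A. The simulation figures show how often such levels are used, not how often anyone would be misdosed, and their upper ends come from scenario 5, where Combination 8 has a true DLT rate of 0.55. The trial schema in Section 5.1 is a figure that could not be seen, so it may carry a note on days.

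**Conclusion.** The contradiction is real and should be corrected. On the schedule in Section 7.4, Tables 7–8 and the flow charts, pralatrexate is 50% above plan at every level below the start, and the first reduction disappears entirely. Arm B is where it matters now: one mucositis or thrombocytopenia DLT in participant 5, or in participant 6 after none in participant 5, sends the next participant to Combination 5.

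The consequence depends on a site taking its days from the operational sections rather than from Section 10.1. The protocol gives no basis for a probability of that, and none is claimed. If it happened, the participant would lose the intended protection and the model would learn about Combination 5 from treatment given at Combination 8. The design, sample size and stopping rules are not in question.

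**What to change.** In Section 7.4, Tables 7 and 8, and a new footnote on the pralatrexate row of the Arm A and B flow charts, state that pralatrexate is given on days 1, 8 and 15 or on days 1 and 15, according to the dose level assigned under Section 10.1. In Table 7, tie 20 mg/m² to days 1 and 15.

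In Section 7.4, make the decitabine days 1–5 or 1–3 by assigned level, to agree with the flow-chart footnotes. The fixed five-day decitabine entries in Tables 8 and 9 need the same change. Section 9.1.7.3 should also say what happens to the Arm A cycle 1 day 8 PK samples at Levels -1 and -2, where no drug is given that day.

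The cost is a text clarification in a few places, with no change to design, sample size or simulations. Until it is issued, the Coordinating Center can write the days of administration into each assignment.
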